16.1 Potential Risks

There are several potential risks to participation in this study. Loss of confidentiality due to the unintended release of sensitive information is one risk. This risk will be mitigated by storing all electronic data on password protected computers. Data will be shared among research partners through REDCap, Mosio, and other secure HIPAA-compliant means (such as secure email). REDCap is a secure, HIPAA-

compliant web-based research data management application, used for building and managing online surveys, and providing a secure electronic database. REDCap will be used as a central location for online study data storage and participant management.

Other potential risks include psychological distress from completing study questionnaires. The contact in the follow-up intervention may also cause emotional distress. Research participants will be reminded at enrollment that they may leave the study at any point with no consequences to the care they receive at SLHS and will be reminded of resources (such as the Hotline) that they can access as needed in the event of psychological distress.

Study staff (including anyone involved in enrollment and informed consent or delivery of the follow-up intervention or outcome measurements, and/or having access to patient-level data) will be trained on the protection of human subjects and HIPAA, with a focus on topics relevant to confidentiality. SLHS staff will assist participants in completing informed consent and baseline surveys, and survey links will be sent out via text or email, or study staff will assist participants in completing surveys over the phone. Study staff at SLHS, University of Washington and the Hotline will have access to protected health information (PHI).

The study is designed to be low burden in terms of participants' time. Patient participants will be compensated for their time. Providers who complete the Provider Satisfaction Survey will not be compensated for their time.

Patients will not be enrolled in the study if a provider or study staff determines that they are unable to consent to participate.

Participants will be under no duress or pressure to participate in or complete this study. Participating in this study will not impact the care they receive, and this will be clearly communicated to participants as part of the informed consent process.

16.2 Potential Benefits

While this study is designed to improve outcomes, there is no guarantee that participants will benefit directly from taking part in the study. Both interventions being tested through this trial are evidence-based, in widespread clinical use, and expected to improve patient outcomes. Patients seen at study clinics have an opportunity to benefit from follow-up with the Hotline, regardless of whether they opt to participate in the proposed research. This study will allow SLHS to improve the quality and consistency of care that individuals screening positive for suicide receive at study sites. Key SLHS providers will be trained on safety planning and connection and support planning. Individuals who consent to participate in the study will receive appropriate monetary compensation for their time (see *Cost/Compensation for Participation* section in this protocol).

The knowledge gained through this study is expected to advance the science of preventing suicide in healthcare settings. We expect the findings of this study to be relevant and of interest to the scientific community, and SLHS Administrators will benefit from information on how best to refine existing clinical protocols for screening for suicide risk.

17. Oversight for Human Subjects Protection & Regulatory Considerations

17.1 Human Subjects Protection

This study will be conducted with oversight from the SLHS Institutional Review Board (IRB). The IRB will review and approve all aspects of the study, including the protocol, informed consent process, and all relevant study-related documents. This includes an initial review and approval process and continuing review as determined by the IRB, as well as review of any modifications made prior to and after initiation of the study. All changes will be approved by the IRB prior to implementation, except where necessary to eliminate apparent immediate hazards to subjects. The Principal Investigator (PI) will be responsible for ensuring compliance with IRB regulations and procedures. All key study personnel will be trained in human subjects' protection. Participation by staff from the University of Washington will be reviewed and monitored by the UW Human Subjects Division.

17.2 Risks to Human Subjects

17.2.1 Involvement of Human Subjects

Suicide constitutes a significant public health concern and is a leading cause of death in the United States.³ However, little is known about health system level interventions to prevent suicide among civilians or adolescents.⁶ This study will fill key gaps in the literature outlined in the *Background* section of the Research Plan. The two treatments being compared in this study are both evidence-based suicide prevention interventions.^{8,9,19-21,56,69} No one will receive a "placebo" or "null" treatment.

17.2.2 Protecting Individuals with Urgent Clinical Needs

This protocol prioritizes individual participants' urgent clinical needs (for example, imminent risk of self-harm) above research related needs or responsibilities. Study staff will be trained that their first responsibility is to protect the safety and wellbeing of study participants (especially those experiencing suicidal crisis or another safety outcome), with duty to the research protocol taking second priority. The independent Research/Medical Monitor (RM) will assist with monitoring this by reviewing situations where individual study participants' needs conflicted with the study protocol. If the RM determines that the participant's needs were not appropriately prioritized, remediation strategies will be developed to modify processes and ensure that participants are better protected in the future. The role and qualifications of the RM are further described in the *Data and Safety Monitoring* section of this protocol.

17.3 Informed Consent Process

When a patient expresses interest in participating in the study, study staff will complete the informed consent process with them. If the patient is younger than 18 years of age, his or her legally authorized representative will provide written permission for the minor to participate in the study; the minor participant will also go through an informed assent process. Participants that assent to study participation prior to age 18 will be reconsented to continue participating if they turn 18 years old while enrolled in the study. Recruitment materials will be written at an age-appropriate reading level to maximize comprehension. Furthermore, the People with Lived Experience with Suicide (PLES) Advisory Board will review the informed consent documents for readability and clarity.

17.3.1 Documentation of Informed Consent

Informed consent (and assent for participants aged 12-17) will be obtained and documented for all primary study participants. Study staff will document each participants' eligibility to participate in the study prior to enrollment. When the participant signs the informed consent/assent documents, the study staff will also sign a form attesting that they have screened for eligibility, reviewed the consent information, and responded to all questions from the participant. The informed consent process will generally be completed in REDCap, and the consent/assent form will be combined electronically with attestation form in a single patient record. All primary data collection for this study will be done electronically, except in the event of technology failure, when paper-based back-up forms may be used.

A waiver of documentation of consent will be requested from the IRB for the patient and provider/staff populations. A consent statement will be included and completion of the survey will constitute consent to participate.

17.4 Bioethics Consultation

The University of Washington's Institute for Translational Health Sciences hosts a Bioethics Consultation Service that will be utilized as needed for the duration of the three-year study. Grant resources have been set aside for an extensive initial bioethics consultation which was completed prior to IRB submission of this protocol, as well as a series of ongoing consultations with bioethicists.

17.5 Inclusion of Women and Minorities

Efforts will be made to recruit females and minorities according to their representation in the research population. There are no exclusion criteria based on sex/gender or minority status. Information about the distribution of races, ethnicities, and gender in our study population (people screening positive for suicide in SLHS Emergency Departments and Primary Care settings) can be found in the *Estimated Final Racial/Ethnic and Gender Enrollment Table*.

Table 5: SPARC Trial Estimated Final Racial/Ethnic and Gender Enrollment

Based on proportion of SLHS patients screening positive for suicide in EDs or primary care settings in 2018³⁴

Race	Male (N)	Female (N)	Total (N)
American Indian/Alaska Native	4	5	9
Asian	3	9	12
Black/African American	6	4	10
Hawaiian/Pacific Islander	2	2	4
White	446	760	1206
Multirace	48	93	141
Ethnicity	Male (N)	Female (N)	Total (N)
Hispanic (Latino/Latina)	45	96	141
Non-Hispanic	463	778	1241

17.6 Inclusion of Minors

Adolescents face a disproportionate burden of suicidal ideation³⁴ compared to adults, and additional evidence is needed to determine the most effective suicide prevention interventions at the health system level for minors.⁵ Adolescents who screen positive for suicide will be included in this study in order to address this critical gap in the literature and begin to develop an evidence base for suicide prevention among adolescents in healthcare settings.

17.7 Cost and Compensation for Participation

Costs of participating in this study include the time participants spend enrolling in the study and completing questionnaires, and the cost of receiving text messages, emails, and phone calls as part of the intervention and/or outcome assessments.

Study participants will receive financial compensation for their time (up to \$125 total over 12 months) in the form of online gift cards. Participants will receive a compensation email including a link to the online gift card following completion of each survey. These funds are intended to compensate participants' time spent discussing sensitive topics and are in no way meant to influence participation in the study. The compensation will be distributed as follows:

- Baseline/Enrollment: \$35
- Two-week satisfaction survey: \$10
- Six-month follow-up: \$40
- 12-month follow-up/study completion: \$40

17.8 Study Discontinuation and Closure

This study may be temporarily suspended or prematurely terminated if there is sufficient reasonable cause. Written notification, documenting the reason for study suspension or termination, will be

provided by the suspending or terminating party to the PI. If the study is prematurely terminated or suspended, the PI will promptly inform all study investigators, study participants, PCORI, and the SLHS IRB, and will provide the reason for termination or suspension. Study participants will be informed, as applicable, of any changes to the study schedule.

The following circumstances may warrant termination or suspension:

- Determination of unexpected significant or unacceptable risk to participants
- Demonstration of efficacy that would warrant stopping
- Insufficient compliance to protocol requirements
- Data that are not sufficiently complete and/or evaluable
- Determination that the primary endpoint has been met
- Determination of futility
- Other reasonable causes not listed here

The study may resume once concerns about safety, protocol compliance, and data quality are addressed to the satisfaction of PCORI, the SLHS IRB, the Data and Safety Monitoring Board (DSMB), and other regulatory or oversight bodies.

17.9 Confidentiality & Privacy

Participant confidentiality and privacy is strictly held in trust by the participating investigators, their staff, the DSMB, the SLHS IRB, and PCORI. This confidentiality is extended to the data being collected as part of this study. Data that could be used to identify a specific study participant will be held in strict confidence within the research team. No personally identifiable information from the study will be released to any unauthorized third party without prior written approval of PCORI and the SLHS IRB.

All research activities will be conducted in as private a setting as possible.

Authorized representatives of PCORI, the DSMB, or SLHS, including the SLHS IRB, may inspect all documents and records required to be maintained by the investigators, including but not limited to medical records for the participants of this study. The clinical study site will permit access to such records for authorized review.

Study participants' contact information will be securely stored for internal use during the study. At the end of the study, all records will be kept in a secure location for 10 years, in accordance with SLHS data retention policy.

Study participant research data, which is for purposes of statistical analysis and scientific reporting, will be transmitted via and stored on REDCap and Mosio, HIPAA compliant web-based platforms. At the end of the study, all study data will be de-identified prior to publication; research data will be archived at SLHS for storage for 10 years.

17.9.1 Measures to Ensure Confidentiality of Shared Data

It is PCORI policy that results and accomplishments of the research that it funds should be made available to the public. The PI will ensure all mechanism used to share data will include proper plans and safeguards for the protection of privacy, confidentiality, and security for data dissemination and reuse (e.g., all data will be thoroughly de-identified and will not be traceable to a specific study participant).

17.10 Study Records Retention

Study records will be retained for 10 years, in accordance with SLHS institutional policy. No records will be destroyed before that time without the written consent of PCORI and/or the SLHS Compliance department.

17.11 Publication & Data Sharing Policy

The SPARC Trial Executive Board will be responsible for developing publication procedures and resolving authorship issues. This study will be conducted in accordance with all PCORI and SLHS data sharing policies and regulations. This trial will be registered at ClinicalTrials.gov, and the results of this trial will be submitted to ClinicalTrials.gov, which ensures that the public has access to the published results of this PCORI-funded research. In addition, results will be submitted for publication in peer reviewed journals. Data from this trial may be requested from other researchers 5 years after the completion of the primary endpoint by contacting the PI. Considerations for ensuring confidentiality of these shared data are described in the 16.9 Confidentiality & Privacy section of this protocol.

17.12 Dissemination of Results

Any publication or presentation of the results of this study will be presented in aggregate form and will not include any patient identifying information.

17.13 Assessing Long-Term Survival

One important outcome of interest in any suicide prevention research is death by suicide. Given the rare nature of this event, we would not expect to see a significant difference in this outcome between the two intervention groups over the duration of this three-year study, thus we have not included death as a primary or secondary outcome for this study. However, the study team plans to follow-up on participants over time in order to assess the effect of these interventions on death by suicide over a 5- 10 year period. National Death Index Plus data from CDC will be obtained for the purpose of assessing death and cause of death of participants enrolled in the study. These data will be accessed only for those participants who are defined in the ITT and the Per-protocol populations for up to ten years following study enrollment.

17.14 Conflict of Interest Policy

The independence of this study from any actual or perceived influence is critical. Therefore, any actual conflict of interest of persons who have a role in the design, conduct, analysis, publication, or any aspect of this trial will be disclosed and managed.

17.15 Protocol Deviations

This protocol defines a protocol deviation as any noncompliance with the clinical trial protocol, International Council on Harmonisation Good Clinical Practice (ICH GCP), or SLHS IRB requirements. The noncompliance may be either on the part of the participant, investigator, study staff, or study site staff. Corrective actions will be developed by the site and implemented promptly in the event of protocol deviations, consistent with ICH GCP:

- Section 4.5 Compliance with Protocol, subsections 4.5.1, 4.5.2, and 4.5.3
- Section 5.1 Quality Assurance and Quality Control, subsection 5.1.1
- Section 5.20 Noncompliance, subsections 5.20.1 and 5.20.2

Study staff will conduct quality assurance monitoring and internal audits on a regular basis. Study staff will be responsible for being vigilant to identify and report deviations in accordance with the SLHS IRB Procedures Manual. All deviations will be addressed in study source documents and reported to the PI; deviations deemed reportable based on criteria in the SLHS IRB Procedures Manual will be reported to the SLHS IRB. Study staff will be responsible for knowing and adhering to the IRB requirements.

17.16.1 Data and Safety Monitoring Board

The Data and Safety Monitoring Board (DSMB) will convene at the beginning of the study to review the protocol, charter, and data reporting tables, then again six months after enrollment begins. The DSMB will meet regularly to review enrollment data and to review data for safety. Additional information on safety monitoring is included in the *Data & Safety Monitoring* section of this protocol.

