6.1 Inclusion & Exclusion Criteria

6.1.1 Selection of Study Sites

All SLHS EDs (n=9) and primary care clinics (n=53) were initially considered for inclusion as study sites. Sites located outside of Idaho (n=1) were excluded. Sites with enough patients screening positive for suicide annually (based on data from 2018) to enroll approximately 40 adults and/or 25 adolescents within approximately 12 months were considered eligible for inclusion.

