12.3 Safety Outcomes

This protocol considers completed suicide, suicide attempts, and inpatient admission in the context of highly suicidal study participants as expected events. These will be routinely tracked as key safety outcomes. The following safety outcomes will be assessed for each participant at 6 and 12 months and reviewed by the Data and Safety Monitoring Board twice annually to determine whether the rate of safety outcomes differs by intervention arm:

- Death by suicide
- Attempted suicide
- Interrupted or aborted suicide attempt
- Psychiatric hospitalization
- Medical hospitalization related to self-harm or attempted suicide

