12.4 Adverse Events and Serious Adverse Events

This protocol does not include tracking of adverse events (AEs). This protocol does not include real-time tracking of serious adverse events (SAEs) for several reasons. First, as stated above, the most important events that would be defined as SAEs are expected safety outcomes in the context of study participants experiencing suicidality. All deaths of study participants will be reviewed and assessed to determine whether the cause of death is suicide. We do not anticipate any SAEs beyond those listed as safety outcomes above, but unanticipated SAEs that occur will be reviewed by the DSMB and the IRB. Second, this research compares two evidence-based interventions that have been widely studied, have an established safety record, and are already in widespread clinical practice, including within SLHS. These are not experimental, novel, or untested interventions with unknown safety outcomes. Finally, the most important safety question to ascertain in the context of this trial is whether rates of safety outcomes or SAEs are differential across the two intervention groups. Given that the two interventions include different types and frequency of contact with study participants, if the study were to monitor AEs and/or SAEs in real-time, differential rates of ascertainment would be expected. Any attempt to compare rates of AEs or SAEs across intervention groups could be substantially biased due to differential ascertainment. Instead, this protocol will monitor safety outcomes collected at 6 and 12 months as part of routine study outcome assessments through regular DSMB meetings to ensure equal ascertainment of outcomes across intervention groups. This is the most valid and reliable way to review safety data in the context of this pragmatic clinical trial.

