13.1 Data Collection

Baseline data are either already collected and recorded in EPIC as standard of care for all patients (demographic data, C-SSRS) or will be completed by the participant via REDCap survey immediately following enrollment and informed consent (Baseline Survey). Outcome data will be collected via REDCap survey or over the phone at 6 months and 12 months. *Table 4* includes a list of all study variables for the primary analysis, the tool to be used for data collection or source of the data, the frequency/timing with which they will be collected, whether they are routinely collected or will be collected specifically for the SPARC Trial, and which entity will collect them. Patient and provider satisfaction surveys will collect additional quantitative and qualitative data and will be collected via REDCap survey.

Table 4: SPARC Trial Variables of Interest and Other Data Elements

Variable	Tool/Source	Routinely collected as standard of care	Mode of contact	Who will collect
Outcomes (6 months)				
Suicidal ideation & behavior	C-SSRS	No	REDCap survey (text, email, or phone)	SLHS
Recent suicide attempts, suicide completion, & self-harm; lethal means	6- and 12-Months Suicide Attempts Survey, Vital Records, EPIC	No	REDCap survey (text, email, or phone)	SLHS
Loneliness	NIH Toolkit Loneliness Scale	No	REDCap survey (text, email, or phone)	SLHS
Uptake of outpatient mental health treatment	Self-report, EPIC, Claims data	Yes	REDCap survey (text, email, or phone)	SLHS

Return to ED for suicidality	Self-report, EPIC, EDIE, Claims data	Yes	REDCap survey (text, email, or phone)	SLHS
Outcomes (12 Months)				
Suicidal ideation & behavior	C-SSRS	No	REDCap survey (text, email, or phone)	SLHS
Recent suicide attempts, completion, & self-harm; lethal means	6- and 12-Months Suicide Attempts Survey; Vital Records, EPIC	No	REDCap survey (text, email, or phone)	SLHS
Loneliness	NIH Toolkit Loneliness Scale	No	REDCap survey (text, email, or phone)	SLHS
Uptake of outpatient mental health treatment	Self-report, EPIC, Claims data	Yes	REDCap survey (text, email, or phone)	SLHS
Return to ED for suicidality	Self-report, EPIC, Claims data, EDIE	Yes	REDCap survey (text, email, or phone)	SLHS

Exposures (Baseline)				
Age in years, age category (adult/peds)	EPIC	Yes	n/a	SLHS
Sex	EPIC	Yes	n/a	SLHS
Race and ethnicity	EPIC	Yes	n/a	SLHS
Address including Zip code of residence (urban/rural)	EPIC	Yes	n/a	SLHS
County of residence (urban/rural)	EPIC	Yes	n/a	SLHS

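### Listed safety outcomes are scheduled only at each participant's own 6- and 12-month points, so the DSMB meeting six months after enrollment begins will have few or none to compare by arm

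*Protocol*

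**What the plan says.** Section 17.16.1 sets the DSMB's calendar: an opening meeting on the protocol, charter and report tables, "then again six months after enrollment begins". After that, "The DSMB will meet regularly to review enrollment data and to review data for safety". Section 12.2 asks the board to look at safety outcomes by arm and by age population, and to decide on early stopping.

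Section 12.3 fixes when those outcomes are available: "safety outcomes will be assessed for each participant at 6 and 12 months and reviewed by the Data and Safety Monitoring Board twice annually". The purpose given there is to see whether rates differ by arm. The list covers suicide death, attempts, interrupted or aborted attempts, psychiatric hospitalisation, and medical hospitalisation for self-harm or attempt. Section 12.4 confirms the route: "this protocol will monitor safety outcomes collected at 6 and 12 months as part of routine study outcome assessments". It rules out AE tracking and real-time SAE tracking, mainly because the arms differ in contact with participants and ascertainment would differ with it. Table 1 (section 7.1) marks safety reporting only in the 6- and 12-month columns.

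Other sources are named. Table 4 (section 13.1) gives the source for attempts, completions and self-harm as "6- and 12-Months Suicide Attempts Survey, Vital Records, EPIC", under the 6-month outcomes, with an equivalent entry at 12 months. Section 9.2 uses vital records for suicide completion, and section 9.3.3 uses EPIC and EDIE for ED visits. Section 12.4 also has all deaths reviewed and sends unanticipated SAEs to the DSMB and IRB.

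The 6-month assessment window is stated two ways: + 4 weeks in section 7, and +/- 4 weeks in section 9.2.

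**The concern.** The DSMB's calendar runs from the first enrollment, whereas the safety outcomes run on each participant's own clock. The first data meeting therefore falls when the earliest enrollee is just reaching the first scheduled safety assessment and almost everyone else is short of it. The board is asked whether safety differs by arm, and it may recommend stopping, in a population selected for suicide risk.

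The arms also differ most in scheduled phone contact during this period. SPI+ calls generally run from day 3 to day 90 (section 10.2), while SP+CC has one call followed by messages (section 10.4). An early difference between arms would arise before any scheduled safety capture.

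The stated reason for having no real-time tracking concerns events learned through study contact. It has much less force against a records query run identically for every randomised participant to one date.

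**Working it through.** The protocol gives no figure for the amount of safety data at any DSMB meeting, so there is none to reproduce. The check is timeline arithmetic.

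**Inputs**
- Total sample: 790 + 592 = 1,382 (section 1.1).
- First data meeting: calendar month 6 (section 17.16.1).
- Accrual period A: not stated. Section 6.1.1 judged sites on capacity to enroll "approximately 40 adults and/or 25 adolescents within approximately 12 months", which suggests 12 months. Section 1.1 gives a 3-year study with 12 months of follow-up, so at most about 36 − 12 = 24 months. I take A = 12, 18 and 24, with uniform accrual, as an assumed range.
- Window opening: 6.0 months after enrollment (section 7), or 6 months minus 28 days, i.e. 6 − 28/30.4375 = 5.08 months (section 9.2).
- Retention: 70%, from the 30% dropout allowance in section 14.2.

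**Formulas for month 6**
- Enrolled = 1,382 × 6/A.
- Person-years at risk = enrolled × 0.25, since mean follow-up is 3 months.
- Participants whose window can have opened = (6 − opening) × 1,382/A. This is 0 for an opening at 6.0 months and 0.92 × 1,382/A for an opening at 5.08 months.

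| Month 6 | A = 12 | A = 18 | A = 24 |
|---|---|---|---|
| Enrolled | 691 | 461 | 346 |
| Person-years | 173 | 115 | 86 |
| Assessable, + 4 weeks | 0 | 0 | 0 |
| Assessable, +/- 4 weeks (ceiling) | 106 | 71 | 53 |
| The same at 70% retention | 74 | 49 | 37 |

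As a share of those enrolled, the ceiling is 0.92/6 = 15.3% whatever A is, or 10.7% at 70% retention. It is reached only if every survey is completed on the day the window opens and there is no lag before the data cut.

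**Next meeting, taken as month 12 from the twice-yearly review**

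| Month 12 | A = 12 | A = 18 | A = 24 |
|---|---|---|---|
| Enrolled | 1,382 | 921 | 691 |
| Reached 6 months | 691 | 461 | 346 |
| The same at 70% retention | 484 | 322 | 242 |

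Half of those enrolled have reached 6 months, or 35% at 70% retention. Early opening of the window would raise the half to at most 6.92/12 = 58%. For A = 12, 1,382 × 0.5 = 691 person-years have accrued. The 691 six-month assessments due cover 691 × 0.5 = 346 of them, again half, before non-response.

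**Reading the sources against this**
Table 4 lists EPIC and vital records as sources, but under the 6- and 12-month outcome headings. The death-review and unanticipated-SAE sentences in section 12.4 carry no 6- or 12-month limit, but they do not provide for a tabulation by arm. No section schedules a records extract before a participant's 6-month point.

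**The case against.** The strongest reply has five parts.

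- **Surveys are not the only source.** A reader might infer that safety outcomes exist only in the surveys. The documents do not support that: EPIC, EDIE and vital records are named, all deaths are reviewed, and unanticipated SAEs go to the DSMB and IRB. The medical monitor, who sits on the board, also reviews PI-flagged staff responses to crises or safety outcomes (section 12.5). This stands. What remains is that none of it is committed to a by-arm compilation before the 6-month point.
- **Accrual is assumed.** A reader might also infer that the board sees no events for most of enrollment. That needs a 12-month accrual, which section 6.1.1 gives only as a site-eligibility screen, and even then it covers only about the first half. With 24 months, 346 of 691 have reached 6 months at month 12, half-way through enrollment, and 691 of about 1,037 at month 18. This stands.
- **The six-month meeting is not only a safety review.** The board also looks at enrollment, retention and data quality, and its charter and report tables, which are not at hand, may specify more. This is fair, but the protocol's own text fixes the safety timing.
- **The choice is reasoned.** Section 12.4 argues for equal ascertainment. Records are not wholly free of the problem: SPI+ calls include risk assessment and support with treatment engagement (section 10.2), so care-seeking in EPIC may partly reflect contact. Section 9.3.4 expects incomplete data from outside SLHS. This limits how early counts can be read, but it is not a reason to withhold them from the board.
- **No gain in detection is shown.** No event rate is given, and section 17.13 expects no significant difference in suicide deaths over the study. This is true, and no claim is made that 86 to 173 person-years would reveal a difference. The point is that a board charged with by-arm safety should see the events already recorded.

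**Conclusion.** The point holds in a limited form. As written, the DSMB meeting six months after enrollment begins will have essentially no scheduled safety outcomes by arm under the + 4 weeks window, and at most about 15% of those enrolled under +/- 4 weeks (about 11% at 70% retention). Between 346 and 691 people would be enrolled by then. At a month-12 meeting about half of those enrolled would have reached 6 months, and fewer would have data after dropout.

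The percentages follow from the meeting dates, the windows and uniform accrual. The head counts also depend on the assumed 24- to 12-month accrual period. The finding does not extend to saying that no safety information could reach the board, or that harm would stay hidden until enrollment is largely complete. It is a weakness in a stated timing rule that can be mended cheaply and should be.

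**What to change.** Add to sections 12.3 and 17.16.1 that, before every DSMB meeting, one identical EPIC/EDIE and vital-records query is run for all randomised participants to a common data-cut date. Report deaths, ED visits for attempt or self-harm, and psychiatric or self-harm admissions, by arm and age group, with person-time. State that the 6- and 12-month assessments remain the primary equal-ascertainment comparison and that the record-based counts are for monitoring. Reconcile the 6- and 12-month windows in sections 7 and 9.2, since the 6-month window decides whether any scheduled data can exist at the first data meeting.

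The cost is a scheduled query about twice a year from sources the protocol already uses. The drawbacks are incomplete capture of care outside SLHS and possible influence of Hotline contact on recorded care-seeking. The report should state both so that early counts are read with caution.
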